 - c. Cutaneous manifestations of immunological disease that do not require systemic immunosuppressive therapy or systemic immunomodulatory therapy need not be excluded (topical steroid treatment is permitted).
22. CD4 (T helper cells), CD8 (cytotoxic T cells), or CD19 (B cells) absolute counts below population-adjusted LLN at Screening or Baseline and confirmed by a repeat test conducted 1 week after the initial test. The population-adjusted LLN for CD4 (T helper cells), CD8 (cytotoxic T cells), and CD19 (B cells) absolute counts are 396, 157, and 74 cells/ μ L respectively. See [Appendix 5](#). (revised per Amendment 02)
 23. Ig (IgG, IgA, or IgM) levels below the LLN at Screening or Baseline, unless both the Investigator and the Medical Monitor agree that the finding is not clinically significant. The assessment of clinical significance will include, but not be limited to, evidence of clinical immunodeficiency. The discussion with the Medical Monitor should include a detailed review of medical history of infections, clinical and laboratory findings. (revised per Amendment 01)
 24. Clinically significant deviation from normal in physical examination, vital signs, or clinically laboratory tests at Screening or Baseline
 25. A prolonged QT/ corrected QT interval (QTc) interval (QTc >450 msec) at Screening or Baseline as demonstrated by average QTc interval from triplicate ECGs. A history of risk factors for torsade de pointes (eg, heart failure, hypokalemia, family history of long QT Syndrome) or the use of concomitant medications that prolong the QT/QTc interval.
 26. Any other abnormality of the ECG at Screening or Baseline (including QRS >110 msec, abnormal electrical axis, PR interval >220 msec and conduction abnormalities) considered clinically significant by the investigator
 27. Left bundle branch block at Screening or Baseline
 28. Persistent heart rate <50 or >100 beats per minute (bpm) at Screening or Baseline
 29. Persistent systolic blood pressure (BP) >165 mmHg or <90 mmHg and diastolic BP >100 mmHg or <60 mmHg at Screening
 30. History of cardiac arrhythmias. Subjects with other heart diseases (eg, ischemic heart disease, clinically significant valvular heart disease) that are not stably and adequately controlled, or uncompensated heart failure (New York Heart Association Class III and Class IV)
 31. Type 1 or Type 2 diabetes mellitus that is not well controlled

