9.4.7 Prior and Concomitant Therapy

Medication (including over-the-counter medications) or therapy administered to the subject before the study (within 6 months of randomization) and during the study (starting at the date of informed consent) will be recorded on the Prior & Concomitant Medication eCRF or Non-Pharmacological Procedures eCRF. The investigator will record on the Adverse Event eCRF any AE for which the concomitant medication/therapy was administered. If the concomitant medication/therapy is being administered for a medical condition present at the time of entry into the study, the investigator will record the medical condition on the Medical History and Current Medical Condition eCRF.

Listings of prohibited and permitted drugs are provided in [Appendix 2](#). Prohibited medications are presented in [Listing 1](#) through [Listing 5](#). Medications that are permitted with restrictions are listed in [6](#) through [Listing 8](#). (revised per Amendment 04)

The following agents are not permitted before randomization (specific timeframes are shown below) and throughout the study until after the last treatment visit: (revised per Amendment 04)

- Drugs which may cause QTc prolongation are not permitted for a period of 5 half-lives or 14 days (whichever is longer) before randomization
- Strong CYP3A4 inhibitors are not permitted for a period of 5 half-lives or 14 days (whichever is longer) before randomization
- Live vaccines are not permitted within 3 months before randomization. This does not apply to non-live/inactivated vaccines
- Ig therapy and biologic drugs are not permitted within 6 months before randomization

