- Medications that are used as needed, rather than on a stable daily basis, and which are central nervous system (CNS) active and may affect cognitive function, are not permitted during a period of 72 hours before cognitive testing

Subjects who initiate treatment with or have dose adjustment of drugs not intended for treatment of cognitive impairment during the study may continue in the study if in the opinion of the investigator this will not interfere with study procedures or subject safety, and are not prohibited above. If the subject initiates treatment for co-morbidities with a (non-prohibited) drug that may affect cognitive function, the subject should not have cognitive assessments performed until the dose has been stable for at least 4 weeks.

Antiplatelet therapy: (revised per Amendment 04)

- For subjects who consent to CSF sample collection: Either aspirin or clopidogrel (or any other antiplatelet drug which is not aspirin) are permitted in all subjects. Aspirin and clopidogrel (or any other antiplatelet drug which is not aspirin) in combination are also permitted but subjects who are on such a combination of antiplatelet drugs may be required to stop 1 or more of these antiplatelet drugs before the LP procedure and restart after the LP as per local guidelines.
- For subjects who do not consent to CSF sample collection: Aspirin and clopidogrel, individually or in combination, are permitted.

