Appendix 2 List of Permitted and Prohibited Prior/Concomitant Medications

Prohibited medications are shown in [Listing 1](#) through [Listing 5](#). Medications permitted with restrictions are listed in [Listing 6 through Listing 8](#). (revised per Amendment 04) **These may not be all-inclusive listings.** Please contact the medical monitor(s) if the investigators have any questions or concerns regarding any medication not listed that your subjects may be taking before enrollment or start during the course of the E2609-G000-202 study.

Antibiotics, analgesics, and anti-inflammatory drugs intended for short courses of treatment are permitted and do not need to follow the restrictions of [Listing 8](#) for a stable dose of 4 weeks before Baseline. If these medications may affect cognitive function but the medications are clinically indicated, then cognitive testing should not take place until at least 72 hours after the last dose of the course of treatment.

Prohibited Prior/Concomitant Medications**Listing 1 Drugs with High Risk of Torsades de Pointes or QTc Prolongation**

| Generic name | Brand name (Names shown are not exhaustive and are examples only; names may be the ® or ™) | Comments |
|---|--|---|
| Prohibited from 14 days (or 5 half-lives, whichever is longer) before Randomization until after the last treatment visit | | |
| Anti-arrhythmic/ abnormal heart rhythm | | |
| Amiodarone | Cordarone; Pacerone | Incidence in females greater than males, Torsades de Pointes risk regarded as low |
| Disopyramide | Norpace | Incidence in females greater than males |
| Dofetilide | Tikosyn | |
| Ibutilide | Corvert | Incidence in females greater than males |
| Procainamide | Pronestyl; Procan | |
| Quinidine | Cardioquin; Quinaglute | Incidence in females greater than males |
| Sotalol | Betapace | Incidence in females greater than males |
| Antihistamine/ allergic rhinitis | | |
| Astemizole | Hismanal | No longer available in United States |
| Terfenadine | Seldane | No longer available in United States |
| Anti-anginal/ heart pain | | |
| Bepridil | Vascor | Incidence in females greater than males |
| Antibiotic/ bacterial infection | | |
| Clarithromycin | Biaxin | |
| Moxifloxacin | Avelox | |
| Sparfloxacin | Zagam | |
| Listing 1 continued | | |
| Antimalarial/ malaria infection | | |
| Chloroquine | Aralen | |
| Halofantrine | Halfan | Incidence in females greater than males |
| Antipsychotic/ anti-emetic/ schizophrenia/ nausea | | |

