| Chlorpromazine | Thorazine | |
| Gastrointestinal stimulant/ heartburn | | |
| Cisapride | Propulsid | |

Listing 1 Drugs with High Risk of Torsades de Pointes or QTc Prolongation

| Generic name | Brand name (Names shown are not exhaustive and are examples only; names may be the ® or ™) | Comments |
|--|--|---|
| Antinausea/ nausea | | |
| Domperidone | Motillum | Not available in the United States |
| Sedative; antinausea/ anesthesia adjunct, nausea | | |
| Droperidol | Inapsine | |
| Antibiotic; gastrointestinal stimulant/ bacterial infection; increase gastrointestinal motility | | |
| Erythromycin | Erythrocin; E.E.S. | Incidence in females greater than males |
| Antipsychotic/ schizophrenia | | |
| Haloperidol | Haldol | When given intravenously or at higher than recommended doses, risk of sudden death, QT prolongation, and torsades increases |
| Mesoridazine | Serentil | |
| Thioridazine | Mellaril | |
| Opiate agonist/ pain control, narcotic dependence | | |
| Levomethadyl | Orlaam | |
| Methadone | Methadose; Dolophine | Incidence in females greater than males |
| Anti-infective/ pneumocystis pneumonia | | |
| Pentamidine | Pentam; NebuPent | Incidence in females greater than males |
| Antipsychotic/ Tourette's tics | | |
| Pimozide | Orap | Incidence in females greater than males |
| Antilipemic/ hypercholesterolemia | | |
| Probucol | Lorelco | No longer available in United States |
| Anticancer | | |
| Arsenic trioxide | Trisenox | Used for leukemia |
| Vandetanib | Zactima | Used for thyroid cancer |

Note: This list is not exhaustive.

QTc = Corrected QT interval.

Listing 2 Prohibited Medications Within 5 Half-lives or 60 days, Whichever is Longer, Before Randomization and Until after the Last Treatment Visit

| Generic name | Brand name (Names shown are not exhaustive and are examples only; names may be the ® or ™) |
|---|--|
| Systemic Immunosuppressants^{a,b} and Immunomodulatory therapy | |
| Azathioprine | Azasan, Imur |
| Ciclosporine | Gengraf, Neoral |
| Dexamethasone | Decadron, Dexasone, Diodex, Hexadrol, Maxidex |
| Fingolimod | Gilenya |
| Methotrexate | Trexall |
| Methylprednisolone | Medrol, Meprolone |
| Mycophenolate | CellCept, Myfortic |
| Prednisolone | Deltasone, Prednicot, Prednisone Intensol, Rayos, Sterapred, Sterapred DS |

Note: This list is not exhaustive.

- a: Topical and inhaled formulations with minimal systemic exposure need not be prohibited.

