
| Generic name | Brand name(s) |
|----------------|--|
| boceprevir | Victrelis |
| clarithromycin | Clarithromycin, clarithromycin extended release, Prevpac |
| cobicistat | Tybost, Stribild, |
| conivaptan | Vaprisol |
| danoprevir | |
| elvitegravir | Vitekta, Stribild |
| indinavir | Crixivan |
| itraconazole | Sporanoz, Onmel |
| ketoconazole | Xolegel, Nizoral, Ketodan |
| lopinavir | Kaletra |
| nefazodone | Serzone |
| nelfinavir | Viracept |
| posaconazole | Noxafil |
| ritonavir | Norvir, Kaletra |
| saquinavir | Invirase, Fortovase |
| telaprevir | Incivek |
| telithromycin | Ketek |
| tipranavir | Aptivus |
| troleandomycin | Triocetin |
| voriconazole | Vfend, Voriconazole |

Note: This list is not exhaustive

Permitted Prior/Concomitant Medications

Listing 6 Medications Which Need To Be on a Stable Dose for 12 Weeks Before the Baseline Cognitive Assessments at Visit 2 and Remain on the Same Stable Dose from Baseline to Final Follow-Up Visit

| Generic name | Brand name (Names shown are not exhaustive and are examples only; names may be the [®] or [™]) |
|----------------------------|---|
| Cognitive Enhancers | |
| Donepezil | Aricept |
| Galantamine | Reminyl |
| Memantine | Namenda |
| Rivastigmine | Exelon |

Note: This list is not exhaustive.

Listing 7 Permitted Medications Used on PRN Basis Which are Not to be Used Within 72 Hours before Cognitive Testing

| Generic name | Brand name (Names shown are not exhaustive and are examples only; names may be the ® or ™) |
|---|---|
| Opiates | |
| Morphine | Astramorph PF, Avinza, Depo Dur, Duramorph, Infumorph, Kadian, MS Contin, MSIR, Oramorph SR, RMS, Roxanol |
| Opiate Agonists | |
| Codeine | Codeine |
| Fentanyl | Actiq, Duragesic, Fentora, Onsolis, Sublimaze |
| Meperidine | Demerol, Meperitab |
| Oxycodone | Dazidox, Endocodone, Eth-OxyDose, OxyContin, OxyFast, OxyIR, Percolone, Roxicodone, Roxicodone Intensol |
| Other opioids or opioid agonists which are used on PRN basis | |
| Benzodiazepines and sedatives | |
| Alprazolam | Alprazolam Intensol, Niravam, Xanax |
| Amitriptyline | (various) |
| Chlordiazepoxide | H-Tran, Librium |
| Clonazepam | Ceberclon, Klonopin |
| Diazepam | Diastat, Dizac, Valium |
| Dothiepin | (various) |
| Estazolam | ProSom |
| Flunitrazepam | Rohypnol |
| Flurazepam | Dalmane |
| Lorazepam | Ativan |
| Midazolam | Versed |
| Olanzapine | Zyprexa |
| Promethazine | Phenergan; others |
| Ramelteon | Rozerem |
| Risperidone | Risperdal |

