| Temazepam | Restoril |
| Triazolam | Halcion |
| Zolpidem | Ambien; others |
| Zopiclone | (various) |
| Other benzodiazepines, tricyclic antidepressants, antipsychotics and other drugs which are used on PRN basis as sedatives | |

Note: This list is not exhaustive

**Listing 7 Permitted Medications Used on PRN Basis Which are Not to be Used
Within 72 Hours before Cognitive Testing**

| Generic name | Brand name (Names shown are not exhaustive and are examples only; names may be the [®] or [™]) |
|--------------|--|
|--------------|--|

PRN = Pro re nata

Listing 8 Permitted Centrally Active or Psychiatric Medications

| Generic Name | Brand name (Names shown are not exhaustive and are examples only; names may be the ® or ™) |
|---|--|
| If to be used on a PRN basis see Listing 7. If to be used chronically, subjects must be on a stable dose for ≥4 weeks before Baseline. Changes in dose or initiation of new concomitant medications for chronic use (not PRN use) is permitted but if the medication affects cognitive function, do not conduct cognitive testing until the dose is stable for 4 weeks. | |
| Antidepressants | |
| Amitriptyline hydrochloride | Elavil |
| Amoxapine | Amoxapine |
| Bupropion | Aplenzin, Budeprion, Buproban, Zyban, Wellbutrin |
| Citalopram | Celexa |
| Clomipramine hydrochloride | Anafranil |
| Desipramine hydrochloride | Norpramin |
| Desvenlafaxine | Pristiq |
| Doxepin hydrochloride | Prudoxin, Silenor, Sinequan, Zonalon |
| Duloxetine | Cymbalta |
| Escitalopram | Lexapro |
| Fluoxetine | Prozac, Sarafem, Selfemra |
| Fluvoxamine | Luvox |
| Imipramine hydrochloride | Tofranil |
| Isocarboxazid | Marplan |
| Maprotiline hydrochloride | Ludiomil |
| Mirtazapine | Remeron Soltab |
| Nortriptyline hydrochloride | Aventyl, Pamelor |
| Paroxetine | Paxil, Pexeva |
| Phenelzine | Nardil |
| Protriptyline hydrochloride | Vivactil |
| Rasagiline | Azilect |
| Selegiline | EMSAM |
| Sertraline | Sertaraline, Zoloft |
| Tranlycypromine | Parnate |
| Trazodone hydrochloride | Desyrel, Oleptro |
| Trimipramine maleate | Surmontil |
| Venlafaxine hydrochloride | Effexor |

Listing 8 Permitted Centrally Active or Psychiatric Medications

| Generic Name | Brand name (Names shown are not exhaustive and are examples only; names may be the ® or ™) |
|---|--|
| Mood Stabilizers (Listing 8 continued) | |
| Carbamazepine | Carbatrol, Epitol, Equetro, Tegretol, Tegretol XR |
| Lamotrigine | Lamictal, Lamictal CD, Lamictal ODT, Lamictal XR |

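### Listing 8 permits four antipsychotics that Listing 1 prohibits for torsades and QTc risk, and the body of the protocol shows that Listing 8 is the error

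*Protocol*

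**What the plan says.** Appendix 2 opens by classing Listings 1 to 5 as prohibited and Listings 6 to 8 as permitted with restrictions.

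- **Listing 1** covers drugs with a high risk of torsades de pointes or QTc prolongation. Its rule is "Prohibited from 14 days (or 5 half-lives, whichever is longer) before Randomization until after the last treatment visit". Chlorpromazine, haloperidol and mesoridazine are among its entries, as is "Thioridazine | Mellaril".
- **Listing 8** covers permitted centrally active or psychiatric drugs. Chronic users must have had a stable dose for at least 4 weeks before Baseline. The header adds "Changes in dose or initiation of new concomitant medications for chronic use (not PRN use) is permitted", subject only to delaying cognitive testing if the drug affects cognition. The same four drugs appear under its Antipsychotics heading, again including "Thioridazine | Mellaril".
- **Section 9.4.7** states "Drugs which may cause QTc prolongation are not permitted for a period of 5 half-lives or 14 days (whichever is longer) before randomization" and carries that ban through the last treatment visit. New starts or dose changes on study are allowed if, in the investigator's opinion, they will "not interfere with study procedures or subject safety, and are not prohibited above".
- **Section 9.3.2**, exclusion 25, removes subjects for a prolonged QTc, for torsades risk factors "or the use of concomitant medications that prolong the QT/QTc interval". Exclusion 37 removes anyone in breach of the concomitant-medication restrictions.
- **Listing 7**, for as-needed drugs, ends its groups with the catch-alls "Other opioids or opioid agonists which are used on PRN basis" and "Other benzodiazepines, tricyclic antidepressants, antipsychotics and other drugs which are used on PRN basis as sedatives". Neither excepts Listing 1 drugs.

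**The concern.** Four drugs are forbidden by name in one listing and allowed by name in another, including as new chronic starts during treatment. A coordinator who looks up haloperidol in Listing 8 gets a clear yes. Appendix 2 sends sites to the medical monitor only for drugs that are not listed, so that route does not apply here.

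The consequences are an ineligible subject randomized, or a subject on study drug given an agent that the protocol bars for torsades risk. The sponsor treats QT as a live issue for this compound. Section 7.1 reports a QTcF increase of 14.9 msec after the single 800 mg dose, although the top dose here is 50 mg, and Section 9.3.3 contains QTcF stopping rules.

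**Working it through.** The protocol states no figure to reproduce. The check is a comparison of lists followed by a reading of the operative text.

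**1. Name match.** Listing 1 has 30 generic names. The Antipsychotics group of Listing 8 has 17 entries.

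| Drug | Listing 1 | Listing 8 |
|---|---|---|
| Chlorpromazine | prohibited | permitted |
| Haloperidol | prohibited | permitted |
| Mesoridazine | prohibited | permitted |
| Thioridazine | prohibited | permitted |
| Pimozide | prohibited | not named |

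- Listing 1 against all of Listing 8: 4 names in common, so 4/30 of Listing 1.
- Share of Listing 8 antipsychotic entries: 4/17 = 23.5%.
- Listing 1 drugs classed there as antipsychotics: 5, of which 4 are in Listing 8.
- Listing 1 against Listing 7, by name: none.
- Listing 5 (strong CYP3A4 inhibitors) against Listing 8: none.

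**2. Can both listings be obeyed?** Listing 8 wants a chronic user stable for at least 4 weeks before Baseline. Listing 1 wants the drug stopped at least 14 days before randomization. Section 9.1.2 puts randomization no more than 10 days after Baseline assessments and eligibility confirmation. A subject stable up to that point has at most 10 days, and 10 < 14. Outside the extension for active infection, the two rules cannot both be met. For a new start on treatment they conflict outright.

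**3. Which listing is wrong?** Section 9.4.7 bans the class and limits new starts to drugs that are not prohibited. Exclusions 25 and 37 point the same way. Nothing in the body text supports Listing 8. The haloperidol comment in Listing 1 describes when risk rises (intravenous or high dose) and does not narrow the ban; the other three drugs carry no comment. The note that the lists are not exhaustive explains omissions, not a drug appearing in two opposing lists.

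**4. How soon would scheduled ECGs show a problem?** Table 7 schedules ECGs at 14 treatment visits, at Weeks 2, 3, 4, 6, 8, 10, 12, 16, 20, 26, 39, 52, 65 and 78. The gaps are 1, 1, 2, 2, 2, 2, 4, 4, 6, 13, 13, 13 and 13 weeks. A drug started just after a late visit could therefore go about 13 weeks before the next scheduled ECG. Visits 15 to 18 have windows of ±10 days, so between two of those visits the gap could reach 91 + 20 = 111 days.

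**5. After deletion.** With the four rows removed from Listing 8, no generic name is in both Listing 1 and Listing 8.

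**The case against.** The best reply is that the operative text already settles the matter. Section 9.4.7 and exclusions 25 and 37 prohibit these drugs, so what remains is a clerical duplication in an appendix whose first listing is clearly headed with the torsades risk.

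Several safeguards also exist:

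- Exclusion 6 removes many subjects likely to be on antipsychotics.
- Exclusion 25 requires an average QTc no higher than 450 msec on triplicate ECGs at Screening and Baseline.
- Concomitant medications are reviewed at almost every visit, and ECGs can be done at unscheduled visits.
- QTcF stopping rules apply.

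These points lower the expected harm, and the protocol gives no expected number of users. They do not remove the defect. A medication review carried out against Listing 8 would pass these drugs, and the stopping rules act only once an ECG has been recorded. The body text shows which entry is wrong; it does not stop a site from following the wrong one.

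A second reply has some force. The Listing 7 catch-alls reach Listing 1 drugs only through class wording. Counting methadone and levomethadyl as opioids gives 4 + 2 = 6 of 30. Reading the sedative and antipsychotic catch-all as broadly would add pimozide and droperidol, giving 8. The count depends on the reading, so 4 of 30 is the figure to rely on. The catch-alls are only a supporting reason for a precedence sentence.

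**Conclusion.** The contradiction is real and should be corrected. Four drugs are both prohibited and permitted by name, and Listing 8 is the wrong entry. The size is 4 of 30 Listing 1 drugs, or 4 of 17 Listing 8 antipsychotic entries (24%).

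The conclusion rests only on the two listings, Section 9.4.7 and the exclusion criteria, and needs no outside assumption. How many subjects would be exposed cannot be estimated from the protocol. The matter concerns safety and eligibility, and it changes no power, type I error or efficacy result.

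**What to change.** Delete chlorpromazine, haloperidol, mesoridazine and thioridazine from Listing 8. Add a sentence to Appendix 2 stating that Listings 1 to 5 take precedence over Listings 6 to 8, including the as-needed catch-alls in Listing 7. Write to sites, and have them check current subjects' medications for these four drugs.

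The text change is four rows and one sentence. Section 11.1 requires a written amendment or administrative change, and an amendment specifically affecting subject safety also needs regulatory submission and ethics approval. The text change could go into the next amendment, but the site letter and medication check should not wait for it. There is a precedent: the revision history for Version 2.0 moved nefazodone between listings because it was in fact prohibited.

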Appendix 3 Pharmacodynamic, Pharmacogenomic, and Other Biomarker Research

Subjects enrolled in this clinical study will have biologic samples collected for PD, PGx, and other biomarker analysis. These samples may be used for discovery and validation to identify biomarkers that may be used for exploratory evaluation of response or safety-related outcomes as well as for use in diagnostic development.

The PGx samples may be used to identify genetic factors that may influence a subject's exposure to the study drug, as well as genetic factors that may have an effect on clinical response or potential AEs related to study drug, and to explore the role of genetic variability in response. Samples may be analyzed to determine a subject's genotypes or sequence for a number of genes or non-coding regulatory regions. The research may include the investigation of polymorphisms in genes that are likely to influence the study drug PK or therapeutic response.

Collection of the PD, PGx, and other biomarker samples will be bound by the sample principles and processes outlined in the main study protocol. Sample collection for PD, PGx, and other biomarker analysis is required as per the study protocol unless the collection and use of the samples is prohibited by specific country laws.

Sample Collection and Handling

The samples will be collected according to the study flow chart. If, for operational or medical reasons, the genomic DNA blood sample cannot be obtained at the prespecified visit, the sample can be taken at any study center visit at the discretion of the investigator and site staff.

Security of the Samples, Use of the Samples, Retention of the Samples

Sample processing, for example DNA or RNA extraction, genotyping, sequencing, or other analysis will be performed by a laboratory under the direction of the sponsor. Processing, analysis, and storage will be performed at a secure laboratory facility to protect the validity of the data and maintain subject privacy.

Samples will only be used for the purposes described in this protocol. Laboratories contracted to perform the analysis on behalf of the sponsor will not retain rights to the samples beyond those necessary to perform the specified analysis and will not transfer or sell those samples. The sponsor will not sell the samples to a third party.

Samples will be stored for up to 15 years after the completion of the study (defined as submission of the clinical study report to the appropriate regulatory agencies). At the end of the storage period, samples will be destroyed. Samples may be stored longer if a health authority (or medicinal product approval agency) has active questions about the study. In

this special circumstance, the samples will be stored until the questions have been adequately addressed.

It is possible that future research and technological advances may identify genomic variants of interest, or allow alternative types of genomic analysis not foreseen at this time. Because it is not possible to prospectively define every avenue of future testing, all samples collected will be single or double coded (according to the ICH E15 guidelines) in order to maintain subject privacy.

Right to Withdraw

If, during the time the samples are stored, a participant would like to withdraw his/her consent for participation in this research, Eisai will destroy the samples. Information from any assays that have already been completed at the time of withdrawal of consent will continue to be used as necessary to protect the integrity of the research project.

Subject Privacy and Return of Data

No subject-identifying information (eg, initials, date of birth, government identifying number) will be associated with the sample. All PD and other biomarker samples will be single coded. Genomic DNA samples used to explore the effects on PK, treatment response, and safety will be single coded. Genomic DNA samples that will be stored for long-term use (defined as 15 years after the completion of the study) will be double coded. Double coding involves removing the initial code (subject ID) and replacing with another code such that the subject can be re-identified by use of 2 code keys. The code keys are usually held by different parties. The key linking the sample ID to the subject number will be maintained separately from the sample. At this point, the samples will be double-coded, the first code being the subject number. Laboratory personnel performing genetic analysis will not have access to the “key.” Clinical data collected as part of the clinical trial will be cleaned of subject identifying information and linked by use of the sample ID “key.”

The sponsor will take steps to ensure that data are protected accordingly and confidentiality is maintained as far as possible. Data from subjects enrolled in this study may be analyzed worldwide, regardless of location of collection.

The sponsor and its representatives and agents may share coded data with persons and organizations involved in the conduct or oversight of this research. These include:

- CROs retained by the sponsor
- IECs or IRBs that have responsibility for this research study
- National regulatory authorities or equivalent government agencies

At the end of the analysis, results may be presented in a final report which can include part or all of the coded data, in listing or summary format. Other publication (eg, in peer-reviewed

scientific journals) or public presentation of the study results will only include summaries of the population in the study, and no identified individual results will be disclosed.

Given the research nature of the PD, PGx, and other biomarker analysis, it will not be possible to return individual data to subjects. The results that may be generated are not currently anticipated to have clinical relevance to the patients or their family members. Therefore, these results will not be disclosed to the patients or their physicians.

If at any time, PD, PGx, or other biomarker results are obtained that may have clinical relevance, IRB review and approval will be sought to determine the most appropriate manner of disclosure and to determine whether or not validation in a Clinical Laboratory Improvement Amendments-certified setting will be required. Sharing of research data with individual patients should only occur when data have been validated by multiple studies and testing has been done in Clinical Laboratory Improvement Amendments-approved laboratories.

